3.2. Subject Grouping

The treatment group for all efficacy and safety analyses will be “SOF/VEL 4 Weeks.”

PK substudy analyses will be presented by SOF/VEL route of administration (“oral” or “nasogastric”) on Study Day 1; and overall (ie, “all subjects”).

3.3. Strata and Covariates

There are no strata or covariates for this study.

3.4. Examination of Subject Subsets

SVR12 will be presented for the SOF/VEL 4 Weeks group by:

- age (< 60 and ≥ 60 years)
- sex at birth (male, female)
- race (White, Asian, Native Hawaiian or Pacific Islander)
- BMI (< 30 or ≥ 30 kg/m²)
- HCV genotype
- IL28B genotype (CC, CT, or TT)
- prior HCV treatment (yes, no)
- completed study drug (yes, no)

3.5. Multiple Comparisons

No multiplicity adjustment will be made since SVR12 is the primary efficacy parameter.

3.6. Missing Data and Outliers

3.6.1. Missing Data

In general, missing data will not be imputed unless methods for handling missing data are specified.

For missing last dosing date of study drug, imputation rules are described in Section 3.8.1. The handling of missing or incomplete dates for adverse event (AE) onset is described in Section 7.1.5.2, and for prior and concomitant medications in Section 7.4.

For analyses of categorical HCV RNA data, missing posttreatment HCV RNA data will have the missing data imputed. Missing on-treatment HCV RNA will have missing data imputed up to the

date of the last dose (for on-treatment displays). If the study day associated with the last dosing date of study drug is greater than or equal to the lower bound of a visit window, and the value at the visit is missing, then the value will be imputed. If the study day associated with the last dosing date is less than the lower bound of a visit window then the on-treatment value at that visit will remain missing.

If an HCV RNA data point is missing and is preceded and followed in time by values that are “<LLOQ target not detected (TND),” then the missing data point will be set to “< LLOQ TND.” If a data point is missing and preceded and followed by values that are “< LLOQ detected,” or preceded by “< LLOQ detected” and followed by “< LLOQ TND,” or preceded by “< LLOQ TND” and followed by “< LLOQ detected,” then the missing value will be set to “< LLOQ detected.” In these situations the data point will be termed a bracketed success; otherwise, the data point will be termed a bracketed failure (ie, \geq LLOQ detected). If a data point is missing and is not bracketed, the missing data point will also be termed a failure (ie, \geq LLOQ detected).

3.6.2. Outliers

Outliers will be identified during the data management and data analysis process, but no sensitivity analyses will be conducted. All data will be included in the data analysis.

3.7. Data Handling Conventions and Transformations

By subject listings will be presented for all subjects in the Safety Analysis Set sorted by subject ID number, visit date, and time (if applicable) unless otherwise specified. Data collected on log forms, such as AEs, will be presented in chronological order within subject.

Age (in years) on the date of the first dose of study drug and sex at birth will be used for analyses and presentation in listings.

If a subject was not dosed with study drug, then the date the informed consent was signed will be used in place of the first dose date of study drug for calculation of age.

Non-PK data that are continuous in nature but are less than the lower limit of quantitation or above the upper limit of quantitation will be imputed as follows:

- A value that is one unit less than the limit of quantitation will be used for calculation of descriptive statistics if the datum is reported in the form of “< x” (where x is considered the limit of quantitation). For example, if the values are reported as < 50 and < 5.0, values of 49 and 4.9, respectively, will be used for calculation of summary statistics. An exception for this rule is any value reported as < 1. For the values reported as < 1 or < 0.1, a value of 0.9 or 0.09, respectively will be used for calculation of summary statistics.
- A value that is one unit above the limit of quantitation will be used for calculation of descriptive statistics if the datum is reported in the form of “> x” (where x is considered the limit of quantitation). Values with decimal points will follow the logic as above.
- The limit of quantitation will be used for calculation of descriptive statistics if the datum is reported in the form of “ \leq x” or “ \geq x” (where x is considered the limit of quantitation).

LabPlus laboratories used COBAS® AmpliPrep/COBAS® TaqMan® HCV Quantitative Test, version 2.0 to determine HCV RNA results in this study. The LLOQ of the assay is 15 IU/mL.

When the calculated HCV RNA IU/mL is within the linear range of the assay, then the result will be reported as the “<< numeric value>> IU/mL.” This result will be referred to in this document as the numeric result or as “≥ LLOQ detected” for categorical results.

When HCV RNA is not detected, the result is reported as “Not Detected” or “target not detected.” This result will be referred to in this document as “< LLOQ target not detected” or “< LLOQ TND.”

When the HCV RNA IU/mL is less than LLOQ of the assay, the result is reported as “< 15 IU/mL.” This result will be referred to in this document as “< LLOQ detected.”

The overall category of HCV RNA < LLOQ includes “< LLOQ TND” and “< LLOQ detected.”

For numerical HCV RNA data, values below LLOQ will be set to the LLOQ – 1 IU/mL (ie, 14 HCV RNA IU/mL). HCV RNA values returned as “target not detected” will also be set to LLOQ – 1 IU/mL. For selected analyses, HCV RNA data (IU/mL) will be transformed to the logarithmic (base 10) scale (\log_{10} IU/mL).

If methods based on the assumption that the data are normally distributed are not adequate, analyses may be performed on transformed data (eg, \log_{10} scale) or nonparametric analysis methods may be used, as appropriate.

Natural logarithm transformation will be used for plasma/blood concentrations and analysis of PK parameters. Plasma concentration values that are below the limit of quantitation (BLQ) will be presented as “BLQ” in the concentration data listing. Values that are BLQ will be treated as 0 at predose time points, and one-half the value of the LOQ at postbaseline time points, where LOQ is corrected for the dilution factor (ie, reported LOQ/dilution factor) for determination of summary and order statistics.

The following conventions will be used for the presentation of summary and order statistics:

- If at least 1 subject has a concentration value of BLQ for the time point, the minimum value will be displayed as “BLQ.”
- If more than 25% of the subjects have a concentration data value of BLQ for a given time point, the minimum and Q1 values will be displayed as “BLQ.”
- If more than 50% of the subjects have a concentration data value of BLQ for a given time point, the minimum, Q1, and median values will be displayed as “BLQ.”
- If more than 75% of the subjects have a concentration data value of BLQ for a given time point, the minimum, Q1, median, and Q3 values will be displayed as “BLQ.”
- If all subjects have concentration data values of BLQ for a given time point, all order statistics (minimum, Q1, median, Q3, and maximum) will be displayed as “BLQ.”

Pharmacokinetic parameters that are BLQ will be imputed as one-half LOQ before log transformation.

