PK concentration values below the lower limit of quantitation (BLQ) will be treated as zero at predose time points, and one-half the value of the lower limit of quantitation (LLOQ) at postbaseline time points, where LLOQ is corrected for the dilution factor (ie, reported LLOQ/dilution factor) for determination of summary and order statistics. For purposes of data presentation, individual values that are BLQ will be presented as “BLQ” in the concentration data listing. For the presentation of summary and order statistics, if at least 1 subject has a concentration value BLQ for the time point, then the minimum value will be displayed as “BLQ”. If more than 25% of subjects have a concentration data value of BLQ for a given time point, then the minimum and the first quartile [Q1] will be displayed as “BLQ”. If more than 50% of the subjects have a concentration data value BLQ for the time point, then the minimum, first quartile [Q1], and median values will be displayed as “BLQ”. If more than 75% of the subjects have a concentration value of BLQ for a given time point, then the minimum, 1st quartile [Q1], median, and 3rd quartile [Q3] values will be displayed as “BLQ”. If all subjects have concentration data values BLQ for the time point, then all order statistics (minimum, first quartile [Q1], median, third quartile [Q3], maximum) will all be displayed as “BLQ”.

Pharmacokinetic parameters that are BLQ will be imputed as one-half LLOQ before log transformation or statistical model fitting.

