8.2.2. Pharmacokinetic Parameters

Pharmacokinetic parameters will be generated for all subjects in the PK substudy analysis set based on intensive PK samples collected on Study Day 1.

The pharmacokinetic parameters for VEL, SOF, GS-566500 and GS-331007 will be computed for all subjects with evaluable PK profiles. For each subject, the following PK parameters will be calculated, as appropriate:

Table 3. Pharmacokinetic Parameters for Each Analyte

Parameter	Description
AUC ₀₋₂₄	area under the concentration versus time curve over the dosing interval
AUC _{last}	area under the concentration versus time curve from time zero to the last quantifiable concentration
C _{last}	last observed quantifiable concentration of the drug in plasma
C _{max}	maximum observed concentration of drug in plasma
C ₂₄	observed drug concentration at the end of the dosing interval
t _{1/2}	estimate of the terminal elimination half-life of the drug in plasma, calculated by dividing the natural log of 2 by the terminal elimination rate constant (λ_z)
T _{last}	time (observed time point) of C _{last}
T _{max}	time (observed time point) of C _{max}
λ_z	terminal elimination rate estimated by linear regression of the terminal elimination phase of the plasma concentration of drug versus time curve

Individual subject concentration data at each timepoint, and individual subject PK parameters for VEL, SOF, and SOF metabolites GS-566500 and GS-331007 in plasma will be listed and summarized using descriptive statistics (n, mean, SD, coefficient of variation [%CV], median, min, max, Q1, and Q3) by route of SOF/VEL administration (PO or NG) on Study Day 1. In addition, for individual subject PK parameter data, the geometric mean, 95% CI, and the mean and SD of the natural log-transformed values will be presented.

Individual concentration data listings and summaries (intensive PK) will include all subjects with concentration data. The sample size for each time point will be based on the number of subjects with nonmissing concentration data at that time point. The number of subjects with concentration BLQ will be presented for each time point. For summary statistics, BLQ values will be treated as 0 at predose and one-half of the lower limit of quantitation (LLOQ) for the analyte being summarized at postdose time points, where LLOQ is corrected for the dilution factor (ie, reported dilution/dilution factor).

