Individual PK parameter data listings and summaries will include all subjects for whom PK parameter(s) can be derived. The sample size for each PK parameter will be based on the number of subjects with nonmissing data for that PK parameter.

The following tables will be provided for each analyte by route of SOF/VEL administration (PO or NG) and overall on study Day 1:

- Individual subject concentration data and summary statistics
- Individual subject plasma PK parameters and summary statistics

The following figures may be provided for each analyte by SOF/VEL route of administration (PO or NG) on Study Day 1:

- Mean (\pm SD) concentration data versus time (on linear and semilogarithmic scales)
- Median (Q1, Q3) concentration data versus time (on linear and semilogarithmic scales)

Mean and median postdose concentration values that are \leq LLOQ will not be displayed in the figures and remaining points connected.

The following listing will be provided:

- PK sampling details (and PK concentrations) by subject that includes both intensive and sparse PK samples

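### C24 values below the limit of quantitation (BLQ) can be given a geometric mean and 95% CI that reflect the half-LOQ constant, and two SAP rules compete for how they are handled

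*SAP*

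**What the plan says.** **Imputation.** SAP 3.7 has: "Pharmacokinetic parameters that are BLQ will be imputed as one-half LOQ before log transformation". Protocol 8.3 agrees: "Pharmacokinetic parameters that are BLQ will be imputed as one-half LLOQ before log transformation or statistical model fitting".

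**Reporting.** For individual PK parameters, SAP 8.2.2 adds to the ordinary descriptive statistics: "the geometric mean, 95% CI, and the mean and SD of the natural log-transformed values will be presented". Tables are by route (oral or nasogastric) and overall. No condition on the BLQ share is attached.

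**C24.** Table 3 of SAP 8.2.2 defines it as the "observed drug concentration at the end of the dosing interval". It is a single measured concentration, taken 24 hours after the first post-transplant dose.

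**Safeguards elsewhere.** SAP 3.7 replaces order statistics of concentrations by BLQ in steps, for example "If more than 50% of the subjects have a concentration data value of BLQ for a given time point" the minimum, first quartile and median are shown as BLQ. The last step covers the complete case: "If all subjects have concentration data values of BLQ for a given time point, all order statistics" become BLQ. In the figures, mean and median postdose values at or below the "LLOQ will not be displayed in the figures and remaining points connected". For the concentration summaries, SAP 8.2.2 adds: "The number of subjects with concentration BLQ will be presented for each time point". None of these rules reaches the geometric mean, log-scale SD or CI in the parameter tables.

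**A second BLQ rule.** SAP 8.2.1, in its paragraph on AUC, has BLQ samples after the first quantifiable one treated as missing in WinNonlin. SAP 8.2.2 bases the n for each parameter on nonmissing values.

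**The concern.** Replacing each BLQ value by the same constant removes variability from the data, and the log-scale SD and t-based interval treat that constant as a measurement. When nearly all C24 values in a group are BLQ, the printed interval describes the imputation rule and not the drug. The SAP guards against this for concentration order statistics and in the figures, but not in the parameter tables, where the geometric mean and CI appear.

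Characterising SOF/VEL pharmacokinetics is a secondary objective (Protocol 2, SAP 1.1), and the summaries are split by route, so groups are smaller than the planned 10. A route group that is wholly unquantifiable at 24 hours could appear as a value with no uncertainty. Separately, the SAP does not say whether a BLQ C24 is imputed or missing, and the two choices give different geometric means.

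**Working it through.** **Inputs from the documents.** n = 10 and 95% confidence (SAP 1.3); BLQ parameter = LOQ/2, then logged (SAP 3.7, Protocol 8.3); grouping by route (SAP 3.2). The only trough variability given is for VEL in another study: CV 47.6% (Protocol Table 1-1), used here as one scenario.

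**Assumptions.** A common LOQ, scaled to 1; lognormal C24; CV 35% to 100%; BLQ share varied, because neither document gives an LOQ or a BLQ rate; a route group of 5 for illustration.

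**The plan's own figure.** No figure is stated for C24. The one sample-size figure, a maximum exact CI length of 63% with n = 10, reproduces: 5 of 10 gives 18.7% to 81.3%, length 62.6%.

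**Formula.** GM = exp(m) and 95% CI = exp(m ± t(0.975, n−1) × s/√n), with m and s the mean and SD of the logs; t = 2.262 for n = 10.

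**1. All BLQ.** Every log is ln 0.5, so s = 0, GM = 0.50 and the CI is 0.50 to 0.50. This holds for any n of 2 or more.

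**2. Nine of ten BLQ.** With the tenth value at 2 x LOQ, m = (9 ln 0.5 + ln 2)/10 = −0.5545 and s = 0.438. The half-width is 2.262 × 0.438/√10 = 0.314. GM = 0.57, CI 0.42 to 0.79, wholly below what the assay can quantify. The result depends on the one measured value: at 1 x LOQ the CI is 0.46 to 0.63; at 10 x LOQ it is 0.34 to 1.33, which is not tight.

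**3. Width and coverage against BLQ share.** 100,000 simulated samples of n = 10. Width is the median ratio of upper to lower limit, imputed against fully observed data; coverage is of the true geometric mean.

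| BLQ share | CV 35%: width, coverage | CV 47.6%: width, coverage | CV 100%: width, coverage |
|---|---|---|---|
| 50% | 2.04 vs 1.60, 80% | 2.21 vs 1.86, 86% | 2.90 vs 3.15, 93% |
| 75% | 1.78 vs 1.60, 58% | 1.85 vs 1.87, 76% | 2.13 vs 3.15, 92% |
| 90% | 1.43 vs 1.60, 49% | 1.45 vs 1.86, 65% | 1.51 vs 3.14, 0% |
| 99% | 1.00 vs 1.60, 5% | 1.00 vs 1.86, 0% | 1.00 vs 3.15, 0% |

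At 50% to 75% BLQ and CV 35% to 47.6% the interval is about as wide as with complete data, or wider, but it is off centre and under-covers. At CV 100% it is narrower, yet coverage stays at 92% to 93%. From about 90% BLQ it is narrower in every scenario and coverage falls well short of 95%.

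**4. Chance of a zero-width CI.** This is p^n for BLQ probability p. For n = 10: 0.75^10 = 5.6% and 0.90^10 = 35%. For n = 5: 0.75^5 = 24% and 0.90^5 = 59%.

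**5. By true median, CV 50% to 100%, n = 10.**
- At 0.5 x LOQ (80% to 93% BLQ): coverage 90% to 99.7%, GM overstated 1.07- to 1.27-fold. This is favourable only because LOQ/2 happens to equal the truth.
- At 0.25 x LOQ (95% to 99.8% BLQ): coverage 0%, GM overstated about 2-fold, 61% to 98% of CIs of zero width.
- At 0.1 x LOQ: GM overstated 5-fold.

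**6. If BLQ C24 is missing instead.** An all-BLQ group has n = 0 and no CI. Otherwise the GM comes from quantifiable subjects only and is overstated by exp(σ φ(z)/(1−p)), where σ² = ln(1 + CV²) and z is the normal quantile of p. For CV 47.6% (σ = 0.452) to 100% (σ = 0.833), that is 1.4- to 1.9-fold at 50% BLQ and 1.8- to 2.9-fold at 75%.

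**The case against.** The best defence is that the SAP already discloses BLQ data. The concentration tables count BLQ subjects at each time point, including 24 hours, the listing shows BLQ, and PK Tables 6-9 print parameters by subject, so ten identical values would be visible beside a zero-width interval. That limits how far a careful reader could be misled. It does not put a BLQ count beside C24 or withhold an uninformative interval.

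Second, the rule in SAP 8.2.1 may mean that a BLQ C24 is never imputed. That reading is possible, although the sentence sits in the AUC paragraph. It replaces one fault with another and shows that the SAP needs to choose.

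Third, Protocol 8.7 makes parameter summaries optional, as appropriate, and refers details to a separate pharmacokinetic plan that is not available here. That plan might settle the matter; the SAP as written does not.

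A reader might infer more than the documents support:
- *That any mostly BLQ C24 looks precise, or that the interval always narrows as fewer values are measured.* Steps 2 and 3 show otherwise.
- *That C24 will be mostly BLQ for some analyte.* Nothing in either document establishes this.
- *That Cmax is equally exposed.* The PK Substudy Analysis Set (SAP 3.1.4) requires calculable parameters, so a subject with nothing quantifiable is unlikely to enter the tables.
- *That the 25/50/75% display thresholds are wrong at their boundaries.* That depends on an assumed quantile definition; the thresholds are a convention shared by the protocol and SAP.

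**Conclusion.** The point holds for C24 in a limited form. Under the half-LOQ rule, a group with every C24 BLQ and a common LOQ is reported as LOQ/2 with a zero-width 95% CI. When nearly all values are BLQ, or the few measured ones lie close to the LOQ, the interval reflects the imputed constant. At 50% to 75% BLQ the possible fault is bias and under-coverage (58% to 93% across the CVs tried), not false precision. Under the competing missing-value rule, the geometric mean is biased upward.

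These sizes rest on a lognormal C24, a common LOQ and assumed BLQ shares; how often the problem would arise cannot be judged from the documents. The consequence is confined to descriptive Day 1 PK tables for a secondary objective. No hypothesis test, SVR12 result or safety summary is affected.

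**What to change.** In SAP 3.7 and 8.2.2, with Protocol 8.3 aligned:

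- **(a)** State which BLQ rule governs C24: the half-LOQ imputation of SAP 3.7 or the missing-value treatment of SAP 8.2.1.
- **(b)** Print number BLQ/N beside C24 in PK Tables 6-9, by route and overall.
- **(c)** Extend the existing BLQ display convention to the parameter tables. When all or most C24 values in a group are BLQ, show the geometric mean, log-scale SD and 95% CI as BLQ or not calculated. More than 50% is a natural cut-off because it matches the existing median rule, but it is a choice that the calculations do not dictate.

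The 25/50/75% thresholds for concentrations can stay as they are, and no rule for Cmax is needed.

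The cost is SAP and protocol wording plus a display condition and a count in four tables. No new data are required. The downside is that some cells will show BLQ where a number would have stood.

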3.8. Visit Windows

3.8.1. Definition of Study Day

Study day is the day relative to the date of the first dose of study drug. Study Day 1 will be defined as the day of the first dose of study drug administration.

Study day will be calculated from the date of first dose of study drug administration and derived as follows:

- For postdose study days: Assessment Date – First Dose Date + 1
- For days prior to the first dose: Assessment Date – First Dose Date

The last dose date of study drug will be the end date for SOF/VEL on the study drug administration eCRF for the record where the “subject permanently discontinued” flag is ‘Yes’.

If there are subjects for whom the date of last study drug is unknown due to the reason that the subject was lost to follow-up and not able to be contacted, the date of last dose will be estimated using the maximum of nonmissing study drug start or stop dates, and on-treatment visit dates and laboratory collection dates (posttreatment visits and unscheduled visits are not included).

3.8.2. Analysis Windows

Subject visits might not occur on protocol-specified days. Therefore, for purposes of analysis, visit windows will be utilized when a single value at a visit is required for analysis.

In general, the baseline value will be the last nonmissing value on or prior to the first dose date of study drug.

HCV RNA, vital signs, and safety laboratory data collected up to last study drug dose date + 3 days will be considered to be on-treatment data; and HCV RNA, vital signs, and safety laboratory data collected after the last dose date + 3 days are considered posttreatment data. The analysis windows for on-treatment HCV RNA, vital signs and safety laboratory data are provided in [Table 1](#).

Table 1. Analysis Windows for On-Treatment HCV RNA, Safety Laboratory Data, and Vital Signs

Visit ID	SOF/VEL 4 Weeks On-Treatment Visit Windows for HCV RNA, Safety Laboratory Values and Vital Signs
Baseline/Day 1 ^a	Date/time of lab sample (date for other) ≤ date/time (date for non-lab) of first dose SOF/VEL
Day 3	2 ≤ Study Day ≤ 4
Day 5	5 ≤ Study Day ≤ 6
Day 7 (Week 1)	7 ≤ Study Day ≤ 11
Day 14 (Week 2) ^a	12 ≤ Study Day ≤ 17
Day 21 (Week 3)	18 ≤ Study Day ≤ 24
Day 28 (Week 4) ^a	25 ≤ Study Day ≤ 41

a Pregnancy testing required at Day 1, Day 14, and Day 28 for SOF/VEL 4 Weeks. Safety Labs include hematology, chemistry, urinalysis, and coagulation. Only the date of assessment is collected for vital signs data.

Pre-transplant CPT and MELD scores and ECGs are to be collected at screening, and pre-surgery (if more than 48 hours between screening visit and start of transplant), and will be listed with their nominal visit with study days assigned.

HCV RNA, vital signs, and safety laboratory data collected after the last dose date + 3 days will be assigned to posttreatment visits. Visit windows will be calculated from the last dose date (ie, FU Day = Collection Date – Last Dose Date) as shown in [Table 2](#).

Table 2. Analysis Windows for Posttreatment HCV RNA, Safety Laboratory Data and Vital Signs

Post-Trt FU Visit ID	Posttreatment Visit Windows for HCV RNA ^a (Days from Date of Last SOF/VEL)	Safety Labs ^b (Days from Date of Last SOF/VEL)	Vital Signs ^c (Days from Date of Last SOF/VEL)
FU-1	4 ≤ FU Day ≤ 10	4 ≤ FU Day ≤ 10	N/A
FU-2	11 ≤ FU Day ≤ 20	11 ≤ FU Day ≤ 20	N/A
FU-4	21 ≤ FU Day ≤ 69	21 ≤ FU Day ≤ 30	4 ≤ FU Day ≤ 30
FU-12	70 ≤ FU Day ≤ 146	N/A	N/A

a SVR follow-up visit window (lower bound) must occur within 7 (SVR4) and 14 (SVR12) days of target, respectively.

b Safety labs will only be summarized up to posttreatment Week 4 (up to 30 days post last dose).

c Vital Signs are only collected at posttreatment Week 4 (summarized up to 30 days post last dose).

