**Criteria for Evaluation:**

**Safety:** AEs and safety laboratory tests will be collected throughout the study (through the Post-treatment week 4 visit).

**Efficacy:** Efficacy will be evaluated using scheduled assessments of HCV RNA performed using Roche COBAS® AmpliPrep/COBAS® TaqMan® HCV Test, v. 2.0.

**Pharmacokinetics:** A single PK blood sample will be collected at each on-treatment visit for all subjects except on Days 1, 3 and 5.

All subjects will be required to participate in an intensive serial PK sub-study to be performed on Day 1. The PK of SOF (and its metabolites GS-566500 and GS-331007), and VEL will be assessed. Serial PK samples will be collected at the following time points: 0 (pre-dose), 0.5, 1, 2, 4, 8, 12 and 24 hours post-dose.

---

---

**Statistical Methods:** The primary efficacy endpoint is the percentage of subjects who achieve SVR12 (HCV RNA < lower limit of quantitation [LLOQ] 12 weeks after stopping study drug) for subjects in the Full Analysis Set (FAS).

Secondary efficacy endpoints include the percentage of subjects who attain SVR at 4 weeks after cessation of treatment (SVR4); the percentage of subjects who have HCV RNA <LLOQ at each on-treatment visit; and the percentage of subjects with virologic failure (VF, defined as HCV RNA  $\geq$  LLOQ at end of treatment or relapse during the Post-treatment follow-up period).

The primary safety endpoint is the percentage of subjects who discontinue from study drug due to an adverse event. Deaths, graft loss, and rejection episodes will also be listed or summarized, as appropriate.

Other endpoints of interest include changes to immunosuppressive therapy and the emergence of viral resistance to SOF or VEL during and after cessation of treatment, and HCV RNA levels (IU/mL) at each on-treatment visit, if relevant.

---

This study will be conducted in accordance with the guidelines of Good Clinical Practice (GCP) including archiving of essential documents.

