#### **8.2.1.2. Safety**

The analysis set for safety analyses will include all subjects who took at least one dose of study drug.

All safety data collected from the first dose of any study drug (including the perioperative dose of SOF/VEL) through the date of last dose of study drug plus 30 days will be included in safety summaries, unless otherwise specified.

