## **8.6. Safety Analysis**

Safety will be evaluated by assessment of clinical laboratory tests, physical examinations, and vital signs measurements at various time points during the study, and by the documentation of AEs.

All safety data collected while “on treatment” (ie, on or after Study Day 1 up to 30 days after the last dose of study drug) will be summarized for subjects who receive SOF/VEL.

Safety endpoints will be summarized as the number (percentage) of subjects with events or abnormalities for categorical data or as an 8-number summary (n, mean, standard deviation, median, Q1, Q3, minimum, maximum) for continuous data.

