**Appendix Table 2. Post-Treatment Study Visits**

Clinical Assessments a	Visit identified by Post-Treatment study week			
	Post-Treatment Week 1 (± 3 days)	Post-Treatment Week 2 (± 3 days)	Post-Treatment Week 4 (± 5 days)	Post-Treatment Week 12 (±5 days)
Weight and Vital Signs b			X	
Adverse Events and Concomitant Medications	X	X	X	
Pregnancy Prevention Counseling	X			
Hematology & Chemistry	X	X	X	X
Coagulation (PT, PTT and INR)	X	X	X	X
HCV RNA and Viral Sequencing Sample (Plasma)	X	X	X	X
Pregnancy Testing c	X	X	X	

a If a subject is in Post-treatment follow-up and undergoes liver transplant, they will continue the follow-up schedule.

b Weight should be done with inner clothing and without shoes. Vital signs include resting blood pressure, pulse, respiratory rate and temperature.

c For females of childbearing potential only: serum β-hCG at Screening, urine test thereafter. If urine is positive, confirm immediately with serum β-hCG.

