7.2. Laboratory Evaluations

Summaries of laboratory data will be provided for the Safety Analysis Set and will include data collected up to the last dose of study drug plus 30 days for subjects who have permanently discontinued the study drug. The analysis will be based on values reported in conventional units. When values are below the lower limit of quantitation, they will be listed as such, and the closest imputed value will be used for the purpose of calculating summary statistics as described in Section 3.7 of this SAP.

A by-subject listing for laboratory test results will be provided by subject ID number and visit in chronological order for screening lab tests, hematology, serum chemistry, and urinalysis separately. Values falling outside of the relevant reference range and/or having a severity grade of 1 or higher on the Gilead Grading Scale for Severity of Adverse Events and Laboratory Abnormalities will be flagged in the data listings, as appropriate.

A listing of the LabPlus laboratory normal ranges will be provided. Ranges are based on the sex and age of the patient on the date of collection of the laboratory sample.

No inferential statistics will be generated.

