7.2.1. Summaries of Numeric Laboratory Results

Descriptive statistics (n, mean, SD, median, Q1, Q3, minimum and maximum) will be provided for the SOF/VEL 4 Week group by analysis visit for: ALT, aspartate aminotransferase (AST), alkaline phosphatase, total bilirubin, direct bilirubin, white blood cell (WBC), neutrophils (absolute), lymphocytes (absolute), reticulocyte count, hemoglobin, platelets, albumin, international normalized ratio of prothrombin time (INR), serum creatinine, and creatinine clearance (CrCl).

A baseline laboratory value will be defined as the last measurement obtained on or prior to the date/time of first dose of study drug. The mean, median, Q1, Q3, minimum and maximum will be displayed to reported number of digits, and SD to reported number of digits +1 for each on-treatment visit. The posttreatment Week 1, 2, and 4 visits will be presented as additional separate visits. In the case of multiple values in an analysis window, data will be selected for analysis as described in Section 3.8.3 of this SAP.

The number and percentage of subjects with at least 1 postbaseline (up to 30 days post last dose) hemoglobin value < 10 g/dL and < 8.5 g/dL will be summarized. The denominator will be the number of subjects with at least 1 postbaseline hemoglobin value.

A listing of subjects meeting the criteria for postbaseline hemoglobin < 10 g/dL and < 8.5 g/dL will be provided.

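### Do the SAP's analysis windows wrongly drop on-schedule Week 4 safety data, or leave the Day 5 and Day 7 HCV RNA rows open to two answers?

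*SAP*

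**What the plan says.** **Week 4 safety row.** Protocol Appendix Table 2 sets the visit tolerance: "Post-Treatment Week 4 (± 5 days". The synopsis adds that "AEs and safety laboratory tests will be collected throughout the study (through the Post-treatment week 4 visit". SAP 3.8.2, Table 2, gives the FU-4 row FU Days 21 to 30 for laboratory tests and 4 to 30 for vital signs, with no FU-12 row for either. Footnote b reads "Safety labs will only be summarized up to posttreatment Week 4 (up to 30 days post last dose"; footnote c reads "Vital Signs are only collected at posttreatment Week 4 (summarized up to 30 days post last dose". SAP 7.2 repeats the limit for laboratory summaries, which "will include data collected up to the last dose of study drug plus 30 days", and SAP 7.2.1 promises that "The posttreatment Week 1, 2, and 4 visits will be presented as additional separate visits". The protocol sets the same limit twice: section 8.2.1.2 covers data "through the date of last dose of study drug plus 30 days will be included in safety summaries, unless otherwise specified", and section 8.6 covers data "up to 30 days after the last dose of study drug". HCV RNA from the same visit has a wider FU-4 window, Days 21 to 69.

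**Early on-treatment HCV RNA rows.** Protocol Appendix Table 1 allows ±2 days for the visits at Days 3, 5 and 7. SAP Table 1 assigns Study Days 2-4, 5-6 and 7-11 to those rows. SAP 3.6.1 imputes an empty row as a success if the results chronologically before and after it are below the LLOQ, and otherwise as a failure. SAP 6.2.2 fills rows by analysis window. Its first paragraph sends missing values to Section 3.6.1; a later paragraph on the same on-treatment analysis cites Section 3.7, which holds no such rule.

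**The concern.** A subject who attends the Week 4 visit on Day 32 has complied with the protocol, yet that subject's laboratory values and vital signs appear in no by-visit summary. FU-4 is the only posttreatment row for vital signs. In a trial of about 10 subjects, losing one or two from the last safety row is noticeable.

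For HCV RNA, the ±2-day tolerances overlap, so compliant visits can leave an early window empty and bring the imputation rule into play. If one programmer brackets the gap with observed samples and another with the single value selected for each neighbouring window, the two can report different Day 5 or Day 7 percentages for a secondary endpoint. The stray reference to Section 3.7 adds to the impression that the rule is unsettled.

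**Working it through.** **Scale.** The plan's own precision figure for 10 subjects is a 95% exact interval of at most 63% in length. Clopper-Pearson at 5/10 gives 18.7% to 81.3%, length 62.6%, which agrees.

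**Week 4 row.** FU Day is collection date minus last dose date (SAP 3.8.2).

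- Permitted days: 28 ± 5 = 23 to 33, which is 11 days.
- Outside a window ending at 30: Days 31, 32 and 33, so 3 of 11.
- HCV RNA: 23 to 33 lies inside 21 to 69, and Week 12 (84 ± 5 = 79 to 89) lies inside 70 to 146. SVR4 and SVR12 lose nothing.

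How often Days 31-33 occur depends on visit scatter, which the documents do not give. Assume a normal distribution around Day 28, rounded to whole days and truncated to 23-33. Let q be the chance per subject; the chance of at least one in 10 is 1 − (1 − q)^10.

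| Assumed SD | q | At least one of 10 |
|---|---|---|
| 1 day | 0.62% | 6.0% |
| 1.5 days | 4.77% | 38.6% |
| 2 days | 10.33% | 66.4% |

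An affected value is not lost. SAP 7.2 and 7.3 list all results by subject, and each summary row shows its n. The plan also leaves other scheduled safety data untabulated: laboratory tests are drawn at posttreatment Week 12 and have no row.

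**Bracketing.** Inputs: Day 3 visit on Study Days 2-5, Day 5 visit on 3-7, Day 7 visit on 5-9, in strict order; Table 1 windows; the record closest to the nominal day, ties to the later (SAP 3.8.3). That section defines nominal day as weeks × 7, so Study Days 3 and 5 are assumed for those rows. Baseline is taken as at or above the LLOQ and Day 14 as below it.

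- Ordered patterns: 47. Patterns with an empty window: 29 (Day 3 in 5, Day 5 in 15, Day 7 in 9).
- Over all 8 combinations of below or not below the LLOQ at the three visits, the two readings can differ in 6 patterns: (3,4,7), (3,4,8), (3,4,9) for the Day 5 row and (2,5,6), (3,5,6), (4,5,6) for the Day 7 row.
- In each of the 6, they differ only if the samples on Days 3 and 4, or on Days 5 and 6, lie on opposite sides of the LLOQ.

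Example: samples on Day 3 (at or above LLOQ), Day 4 (below) and Day 7 (below). The Day 3 row takes the Day 3 sample and the Day 5 window is empty. Observed samples (Days 4 and 7) give a success; window-selected values (Days 3 and 7) give a failure.

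With independent normal scatter of SD 1 day around each target, the patterns have probability 9.89% (Day 5 row) and 12.50% (Day 7 row), together 22.39%. If the chance of crossing the LLOQ between the two consecutive days is 5% to 30% (also an assumption), the chance of a difference per subject is 0.2239 × 0.05 = 1.1% to 0.2239 × 0.30 = 6.7%. In 10 subjects that is 0.11 to 0.67 expected. One such subject changes, for example, 9/10 (95% CI 55.5% to 99.7%) to 8/10 (44.4% to 97.5%).

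**The case for a change.** The best case for a change is that both points arise with full compliance and both could be settled with a few words and no new data. Protocol 8.2.1.2 allows exceptions to the 30-day limit, the Week 4 row is promised in SAP 7.2.1, and listings are not summaries. On bracketing, SAP 3.6.1 and 6.2.2 do speak of visits and of values assigned by window. The window-selected reading can also impute a success over an observed result at or above the LLOQ: dates 3, 4 and 7 with only the Day 4 sample at or above it.

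The facts in that case stand; the need for a change does not follow. A visit tolerance says when a subject may attend, not what is summarised. Protocol 8.6 states the 30-day limit without the exception clause, and adverse event reporting and the treatment-emergent definition stop at the same point. If the row ran to Day 33, a Day 32 hemoglobin would enter the Week 4 row but not the counts below 10 and 8.5 g/dL in SAP 7.2.1.

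On bracketing, the phrases set against each other do different jobs. One says when a row needs imputing and another how rows are filled. Only the chronological wording, which protocol 8.3 shares, says what brackets a gap, and in time most naturally means the samples actually drawn. The Section 3.7 citation is a slip, since the first paragraph of SAP 6.2.2 already names 3.6.1 for the same analysis.

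**Conclusion.** No change to the plan follows. The Day 30 limit is a fair trade-off. It can leave an on-schedule Week 4 visit out of one descriptive row (3 of 11 permitted days; 6% to 66% chance of at least one in 10 subjects under assumed scatter of 1 to 2 days). In return it keeps one safety cut-off throughout, and the values remain in the listings.

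The bracketing point is a detail that an analyst fills sensibly by using observed samples, together with a wrong section number. The other reading would alter only the Day 5 or Day 7 row of the on-treatment table, in 6 of 47 date patterns and with a consecutive-day LLOQ crossing: about 1% to 7% per subject under the stated assumptions, 10 percentage points per affected subject. That is small beside intervals up to 63 points long, and SAP 6.1.2 plans no hypothesis test. SVR4, SVR12, the Day 3 row, the Day 14 to 28 rows and numeric HCV RNA do not depend on the reading.

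The pattern counts follow from the documents plus the assumed nominal days and the assumed baseline and Day 14 status. The probabilities rest on assumed scatter and crossing rates.
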